3.1.1. Screening Period

Before any study-specific procedures are performed, the appropriate written informed consent must be obtained (see Section 9.2). To assess subject eligibility, all screening assessments, as listed in the Time and Events Table (Table 6-1), should be completed. A Screening Period of up to 12 weeks will allow subjects to achieve disease control (ie, no new lesions for ≥ 2 weeks) using a stable dose of 20 mg/day up to 120 mg/day (or 1.5 mg/kg/day, whichever is higher) of oral prednisone/prednisolone for ≥ 2 weeks. Once disease control has been attained, subjects may be randomized to treatment, provided they continue to fully satisfy the eligibility criteria. Refer to the study procedures manual (SPM) for retesting and/or rescreening procedures.

3.1.2. Treatment Period

Subjects who meet all eligibility criteria will be randomized 1:1 to receive either ofatumumab SC or placebo; all doses of investigational product will be administered at the study center once every 4 weeks under the observation of the investigator, with the first dose (Week 0) signifying the start of the 56-week Treatment Period.

During the 56-week Treatment Period, site personnel will administer all doses of investigational product in the clinic. Subjects must be treated with acetaminophen/paracetamol and an antihistamine (cetirizine or equivalent) 1 to 2 hours prior to each administration of investigational product to lessen the likelihood of localized reactions.

Subjects will remain on the stable daily oral steroid dose achieved during the Screening Period until Week 2, when they will begin tapering their steroid dose with the goal of reducing or eliminating the daily use of steroids. Subjects' daily oral steroid dose will be reduced by 1 dose level every 2 weeks (as illustrated in [Table 3-2](#)) until the onset of disease flare/relapse. For a subject who experiences disease flare/relapse, the prednisone/prednisolone dose will be increased by 1 to 4 levels per week until disease control is achieved (ie, no new lesions for ≥ 2 weeks); the prednisone/prednisolone taper will then be reinitiated after a 2-week period of disease control.

Table 3-2 Oral Prednisone/Prednisolone Dose-taper Schedule

Current Dose	Next Taper Dose ^a (every 2 weeks)	Increase Dose for Flare/Relapse ^b (increase by 1 to 4 levels per week)				Dose for Post-Flare Taper
		1 level	2 levels	3 levels	4 levels	
160	140	180	200	220	240	Decrease dose by 1 level after 2 weeks of disease control, then return to standard taper schedule.
140	120	160	180	200	220	
120	100	140	160	180	200	
100	80	120	140	160	180	
80	60	100	120	140	160	
60	50	80	100	120	140	
50	40	60	80	100	120	
40	30	50	60	80	100	
30	25	40	50	60	80	
25	20	30	40	50	60	
20	17.5	25	30	40	50	
17.5	15	20	25	30	40	
15	12.5	17.5	20	25	30	
12.5	10	15	17.5	20	25	
10 ^c	7.5	12.5	15	17.5	20	
7.5	5	10	12.5	15	17.5	
5	2.5	7.5	10	12.5	15	
2.5	0	5	7.5	10	12.5	
0	0	2.5	5	7.5	10	

- Prednisone/prednisolone is reduced by 1 dose level every 2 weeks, with the goal being elimination of prednisone/prednisolone. For subjects at a starting dose >160 mg, taper dose by 20 mg every 2 weeks until the dose is 160 mg, at which point the decrements shown on the table above should be used.
- Subjects will remain on the standardized oral prednisone/prednisolone taper schedule until disease flare/relapse. In the event of disease flare/relapse, oral prednisone/prednisolone will be increased by a rate of 1 to 4 levels per week until disease control is re-established. The oral prednisone/prednisolone taper will then be reinitiated after disease control is maintained for 2 weeks.
- Once the dose is reduced to 10 mg, an attempt at reducing the steroid dose further need only be attempted until the first flare/relapse occurs. In the event of a flare/relapse at a prednisone/prednisolone dose of ≤10 mg/day, the dose will be temporally increased in order to re-establish disease control (no new lesions for >2 weeks); after disease control is maintained, further steroid tapering attempts to <10 mg will be at the investigator's discretion.

3.1.3. Follow-up Period

Subjects will be followed-up for a minimum of 4 weeks after the last dose of investigational product at the Week 56 visit. The follow-up visit will include B-cell counts and other safety, efficacy, and quality of life assessments.

If B-cell counts have not recovered by the Week 60 visit, subjects not entering the extension study (OPV117059) will remain in Individualized Follow-up until:

- CD19+ B-cell counts and circulating IgG levels are \geq LLN or baseline levels (if $<$ LLN)
- Other criteria for study withdrawal/exit are met (see Section 4.4.3)
- Two years after the last dose of investigational product (whichever comes first).

The Individualized Follow-up assessments should be scheduled approximately every 12 weeks. Subjects who withdraw from treatment will also enter the Individualized Follow-up Period.

Note: Subjects who are hepatitis B surface antigen (HBsAg) negative, hepatitis B core antibody (anti-HBc) positive, and hepatitis B virus (HBV) DNA negative (or if in Japan and HBsAg negative, anti-HBc (HBcAb) negative, but hepatitis B surface antibody [HBsAb] positive) must continue HBV DNA polymerase chain reaction (PCR) monitoring at a minimum of every 12 weeks for 6 months after the last dose of study treatment.

For subjects who participate in the extension study, OPV116910 (also known as COMB157J2301) Week 60 study assessments will be completed before any study-related assessments are performed for the extension study.

3.1.4. Pharmacokinetic-Pharmacodynamic Substudy

This protocol includes a substudy to determine the pharmacokinetics and pharmacodynamics of ofatumumab SC in subjects with PV. The substudy will be conducted at selected study centers and will enroll approximately 25 subjects. Subject participation in the substudy is optional and requires informed consent. A subject may be enrolled in the primary study whether or not he/she chooses to participate in the substudy.

The Time and Events Table for the substudy-specific visits and sampling time points is provided in [Table 6-3](#). An attempt should be made to draw pharmacokinetic samples at the same time of day as administration of the first dose of investigational product.

3.2. Discussion of Design

The design of the study has taken into account the low incidence and chronic relapsing nature of PV, and the fact that therapy with corticosteroids—albeit associated with significant side effects—represents the standard of care for management of PV. The study is designed to evaluate the efficacy of ofatumumab SC in an environment where a subject requiring corticosteroids is undergoing a taper towards minimal treatment or, ideally, no treatment with systemic steroids. For this reason, the study has been designed to add the randomized study treatment (1 group receiving ofatumumab SC and the other group receiving placebo) over a background of tapering steroids in all subjects.

The dosing duration of 1 year will allow adequate time to assess time to remission in both study groups. Historical data indicate that remission can be expected in approximately

54% of subjects in the placebo group (with steroid dose adjustment), and in about 80% of subjects in the ofatumumab SC group [Beissert, 2010].

When administered via IV infusion, ofatumumab has been associated with infusion reactions that have occasionally led to temporary interruption or withdrawal of treatment. To reduce such reactions, premedication with acetaminophen/paracetamol, oral or IV antihistamine, and oral and/or IV glucocorticoids has been used in clinical studies involving oncology and rheumatoid arthritis populations. In the current study, to lessen the likelihood of localized reactions with administration of ofatumumab SC, oral doses of acetaminophen/paracetamol and antihistamine will be administered 1 to 2 hours prior to the administration of investigational product. All subjects (ofatumumab SC and placebo groups) will be premedicated in order to maintain blinding and to minimize confounding variables on dosing days.

[figure not shown]
Within the protocol, reference to Novartis is inclusive of tasks and responsibilities that will be performed by a contract research organization (eg, [REDACTED]).

3.3. Dose Rationale

For Study OPV116910, an ofatumumab SC dose of 20 mg will be administered every 4 weeks through Week 56 (with an additional 20-mg 'loading' dose [ie, 40 mg total] at both Week 0 and Week 4). This dose was selected on the basis of the following factors: safety and tolerability from studies conducted in other autoimmune indications (rheumatoid arthritis and RRMS), B-cell depletion/repletion data from a single SC dose study (GSK Study OFA110867; N=6/arm) in subjects with rheumatoid arthritis, newly-available data from a large Phase II repeat-dose (up to 20 weeks) study in subjects with RRMS (GSK Study OMS112831; N=232), and pharmacometric modeling.

The original dose rationale proposed an ofatumumab SC dose of 60 mg every 12 weeks; however, in the ongoing Phase II RRMS study (GSK Study OMS112831), ofatumumab SC doses of 3 to 60 mg every 12 weeks were not found to completely suppress B cells during the inter-dosing interval (Figure 3-3). However, when dosed every 4 weeks, ofatumumab suppressed B cells to below the limit of quantification during the inter-dosing interval in more than 90% of subjects.

Figure 3-3 Observed Median and Inter-decile Range B-cell Depletion for Ofatumumab SC in GSK Study OMS112831

[figure not shown]
Abbreviations: LLN=lower limit of normal; LLQ=lower limit of quantitation; SC=subcutaneous.

Achieving adequate B cell depletion is viewed as essential for maintenance of efficacy in PV [Eming, 2008; Mouquet, 2008], although no threshold for B cell depletion has been demonstrated. This fact notwithstanding, suppression of B cells to levels seen with off-label rituximab is desirable to ensure comparable efficacy, particularly during a period of steroid withdrawal. On the basis of observed B-cell suppression with doses of 3, 30, and 60 mg and pharmacometric modeling, dividing the dose to administer ofatumumab SC 20 mg every 4 weeks, rather than 60 mg every 12 weeks, is anticipated to achieve that goal.

The predicted median B cell depletion and the predicted median percentage B cell inhibition, complete with inter-decile ranges, are shown in Figure 3-4 and Figure 3-5 (n=1000 per simulation), respectively. At steady-state (Week 12), the predicted median inhibition is 99%, with 90% of subjects achieving B cell inhibition greater than 97.5%, as indicated by the shaded region. To help achieve a rapid onset of clinical effect, loading doses of 40 mg (as two 20-mg SC injections) will be administered at Weeks 0 and 4.

[figure not shown]
The current dosing regimen is expected to rapidly deplete B-cells and maintain the desired level of suppression during the inter-dosing intervals in the majority of subjects in order to maintain disease remission once achieved. After dosing ceases, the predicted median time to replete to the LLN (110 cells/uL) in subjects with PV is approximately 28 weeks.

Figure 3-4 Predicted Median and Inter-decile Range B-cell Depletion with Ofatumumab SC 40 mg Administered at Weeks 0 and 4, then 20 mg Administered Every 4 Weeks Through Week 56

Abbreviations: LLN=lower limit of normal; LLQ=lower limit of quantitation; SC=subcutaneous.

Figure 3-5 Predicted Median and Inter-decile Range B-cell Percent Inhibition with Ofatumumab SC 40 mg Administered at Weeks 0 and 4, then 20 mg Administered Every 4 Weeks Through Week 56

Abbreviation: SC=subcutaneous.

With respect to safety and tolerability, all doses in GSK Study OMS112831 were well tolerated and there were no new or unexpected safety findings during the Treatment Period (follow-up was ongoing as of January 2014). Administration of ofatumumab SC in subjects with PV is also anticipated to be well-tolerated.

In summary, on the basis of results of the repeat-dose study in subjects with RRMS and subsequent dose modeling, administration of ofatumumab SC 20 mg every 4 weeks (with an additional dose at Weeks 0 and 4 in order to reach steady-state more quickly during initial steroid-tapering) should provide more consistent B-cell suppression in subjects with PV than the previously-proposed dose regimen of 60 mg administered every 12 weeks.

4. SUBJECT SELECTION AND WITHDRAWAL CRITERIA

Before subjects may be entered into the study, Novartis requires a copy of the site's written institutional review board (IRB)/independent ethics committee (IEC) approval of the protocol, informed consent form, and all other subject information and/or recruitment material, if applicable (see Section 9.2). All subjects must personally sign and date the consent form before any subsequent screening procedures may be performed.

A subject will be considered enrolled once a randomization number is assigned. A subject may only be randomized once, and each randomization number may only be assigned to 1 subject.

4.1. Number of Subjects

Approximately 136 subjects (68 subjects per treatment group) will be enrolled into the study, which accounts for a drop-out rate of $\leq 13\%$ (see Section 8.2.1). Approximately 48 sites in approximately 15 countries are expected to participate in this study.

4.2. Inclusion Criteria

Specific information regarding warnings, precautions, contraindications, AEs, and other pertinent information on the Novartis investigational product or other study treatment that may impact subject eligibility is provided in the [Investigator's Brochure](#) [Ofatumumab/OMB157/GSK1841157 Investigator's Brochure, 2016].

Deviations from inclusion criteria are not allowed, as they can potentially jeopardize the scientific integrity of the study, regulatory acceptability, or subject safety. Therefore, adherence to the criteria as specified in the protocol is essential.

It is the investigator's responsibility to confirm that potential subjects are willing and able to provide written informed consent, participate in the study as an outpatient, make frequent visits to the study center during the Treatment and Follow-up Periods, and comply with all study requirements including restrictions on usage of concomitant medications and other treatments.

To be eligible for enrollment in the study, subjects must meet all of the following criteria:

All Subjects

1. Adults (18 through 70 years of age) with clinically-documented diagnosis of PV for >2 months and <10 years.
2. History of biopsy consistent with PV (H and E staining and direct immunofluorescence). If no history, a biopsy may be performed during the Screening Period.
3. At least 1 previous episode of a failed steroid taper (ie, disease flare/relapse) at a prednisone/prednisolone dose >10 mg/day, with a Pemphigus Severity of Clinical Disease score of moderate (2) or severe (3) (may be historical/retrospective assessment [see [Appendix 6](#) and SPM for guidance]), where severity of disease at flare/relapse necessitated an increase of >20 mg/day. *Note: prednisone/prednisolone dose should not be increased for the sole purpose of entry into this study.*

Additional Criteria Prior to Randomization

4. Screening anti-Dsg antibodies consistent with a diagnosis of PV (ie, elevated anti-Dsg3 antibodies).
5. Has initiated and received a stable dose of prednisone/prednisolone from a minimum of 20 mg/day (eg, 0.25 mg/kg/day for an 80-kg person) up to a maximum of 120 mg/day or 1.5 mg/kg/day (whichever is higher) for ≥2 weeks prior to randomization. (*Note: subjects who are on every-other-day dosing regimens need to change to a daily dosing regimen for ≥2 weeks during the Screening Period in order to qualify.*)
6. Has exhibited PV disease control, defined as no new lesions for ≥2 weeks.

Additional Criteria for Female Subjects

7. A female subject is eligible to enter the study if she:
 - a. Is of nonchildbearing potential, who is documented as either surgically sterile (bilateral tubal ligation, bilateral oophorectomy, or post-hysterectomy) or is postmenopausal without menses for >2 years. Women who are <2 years postmenopausal are required to have menopausal status confirmed by follicle-stimulating hormone (FSH) and estradiol levels at the screening evaluation. If FSH and estradiol levels do not provide confirmation of menopause, subject will be considered to be of childbearing potential.
 - b. Is of childbearing potential, defined as a woman who has functional ovaries, ducts, and a uterus with no documented impairment that would cause sterility. This includes women with oligomenorrhea (even severe), women who are perimenopausal, and women who have just begun to menstruate. Subject must:
 - Have a negative serum pregnancy test at screening
 - Agree to the consistent and correct use of acceptable methods of contraception during heterosexual intercourse, beginning when the subject provides

informed consent and lasting until 12 months after last dose of investigational product. Acceptable methods of contraception are limited to the following:

- Oral contraceptives (either combined or progesterone only)
- Injectable progesterone
- Levonorgestrel implants
- Estrogenic vaginal ring
- Percutaneous contraceptive patches
- Intrauterine device or intrauterine system with a documented failure rate of <1% per year
- Male partner sterilization (vasectomy with documentation of azoospermia) prior to the female subject's entry into the study; this male must be the subject's sole partner
- Double-barrier method: condom and an occlusive cap (diaphragm or cervical/vault caps) with a vaginal spermicidal agent (foam/gel/film/cream/suppository)
- Complete abstinence from heterosexual intercourse, when this is in line with the preferred and usual lifestyle of the subject
- ** In Japan, refer to [Appendix 2](#) for applicable country-specific clarifications regarding acceptable methods of contraception for subject inclusion in this study.**

In **France**, a subject will be eligible for inclusion in this study only if either affiliated with, or a beneficiary of, a social security category.

4.3. Exclusion Criteria

Deviations from exclusion criteria are not allowed because they can potentially jeopardize the scientific integrity of the study, regulatory acceptability, or subject safety. Therefore, adherence to the criteria as specified in the protocol is essential.

Subjects meeting any of the following criteria will not be enrolled:

1. Diagnosis of pemphigus foliaceus, paraneoplastic pemphigus, or other autoimmune blistering disease (other than PV).
2. Past or current history of hypersensitivity to components of the investigational product or medically significant adverse effects (including allergic reactions) from cetirizine (or antihistamine equivalent) or paracetamol/acetaminophen.
3. Prior treatment with rituximab without achieving disease control within 6 months of initiating rituximab dosing.

4. Prior treatment with any of the following within the specified periods:

Medication and Other Treatment Restrictions Prior to Randomization

Any time	6 weeks	8 weeks ^a	6 months	18 months
Ofatumumab, total body irradiation, bone marrow transplantation, anti-CD4	Live vaccine	Immunosuppressive or immunomodulatory agents, including: – azathioprine – cyclosporine – dapsone – mycophenolate – methotrexate – tacrolimus	– cyclophosphamide – cladribine – plasmapheresis – immunoabsorption or immunoglobulin therapy – alemtuzumab – mitoxantrone	Rituximab or other anti-CD20 treatments

5. Confirmed PML, or neurological findings potentially consistent with PML (see [Appendix 4](#) and [Appendix 5](#)).
6. Evidence or history of clinically significant infection including:
- Chronic or ongoing active infectious disease requiring long-term systemic treatment, including, but not limited to, chronic renal infection, chronic chest infection with bronchiectasis, or active hepatitis C.
 - Positive test for HBsAg. For HBsAg negative, but anti-HBc/HBcAb positive (regardless of HBsAb status), an HBV DNA test will be performed and the subject will be excluded if results are positive. Consult with a physician experienced in the care and management of subjects with hepatitis B to manage/treat subjects who are anti-HBc positive.
 - History of positive serology for human immunodeficiency virus.
 - Previous serious opportunistic or atypical infections.
 - Prior history, or suspicion, of tuberculosis (TB).
 - ** In Japan, refer to [Appendix 2](#) for additional country-specific screening procedures and exclusion criteria for TB, Pneumocystis pneumonia, and hepatitis B.**
7. Past or current malignancy, except for:
- Cervical carcinoma Stage 1B or less.
 - Noninvasive basal cell and squamous cell skin carcinoma.
 - Cancer diagnoses with a duration of complete response (remission) >5 years.
Note: A history of hematologic malignancy excludes a subject from participation, regardless of response.
8. Significant concurrent, uncontrolled medical condition that could affect the subject’s safety, impair the subject’s reliable participation in the study, impair the evaluation of endpoints, or necessitate the use of medication not allowed by the protocol.

9. Any of the following screening laboratory values:
 - White blood cells <3.8 GI/L ($<3800/\text{mm}^3$).
 - Neutrophils <2 GI/L ($<2000/\text{mm}^3$).
 - Platelets <130 GI/L ($<130,000/\text{mm}^3$).
 - Circulating IgG, IgA, or IgM levels $<10\%$ of the LLN and requiring treatment in the opinion of the investigator.
 - Alanine aminotransferase (ALT) >2.0 times the upper limit of normal (ULN).
 - Aspartate aminotransferase $>2.0 \times$ ULN.
 - Alkaline phosphatase $>1.5 \times$ ULN.
 - Bilirubin $>1.5 \times$ ULN (except in cases of isolated predominantly indirect hyperbilirubinemia due to Gilbert's syndrome).
10. Use of an investigational drug or other experimental therapy within 4 weeks, 5 pharmacokinetic half-lives, or the duration of biological effect (whichever is longer) prior to Screening.
11. Electrocardiogram (ECG) showing a clinically significant abnormality or showing a corrected QT interval (QTc) ≥ 450 msec (≥ 480 msec for subjects with a bundle branch block) (ECG to be obtained during Screening/prior to receiving the first dose of study drug).
12. Woman who is breastfeeding.

4.4. Withdrawal Criteria

4.4.1. Dose-holding Criteria

Investigational product dosing will be held in the following situations:

- Neutropenia with an absolute neutrophil count <1 GI/L ($<1000/\text{mm}^3$; $<1.0 \times 10^9/\text{L}$) (ie, Grade 3 and higher [CTCAE, 2013]).
- Suspected serious systemic infection.
- Positive symptoms on neurological symptoms questionnaire (see [Appendix 4](#) and [Appendix 5](#)).

If the condition resolves within 1 week, administer the held dose and then return to the regular dosing schedule. If the condition does not resolve within 1 week after a held dose, skip that dose; after the condition resolves, return to the regular dosing schedule. Consult with the medical monitor if a subject misses 2 or more consecutive doses.

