11.4. Appendix 4 – Algorithm for PML Monitoring

Monitoring for progressive multifocal leukoencephalopathy (PML) will be an important part of the safety monitoring for this study.

PML is a viral-induced demyelinating disease of the central nervous system usually occurring in the immunocompromised individual and has been reported with ofatumumab. JC virus (JCV) infection resulting in PML and death has been reported in rituximab-treated subjects with hematologic malignancies or with systemic lupus erythematosus, an indication for which rituximab has not been approved. Investigators and nurses should pay careful attention for signs and symptoms consistent with a diagnosis of PML. Signs and symptoms of PML include visual disturbances, ocular movements, ataxia, and changes in mental status such as disorientation or confusion.

[figure not shown]
These symptoms are not an exhaustive list, and the investigator should exercise judgment in deciding to report signs and symptoms to Sponsor promptly. If a subject develops neurological signs or symptoms consistent with PML, treatment should be halted and the subject referred to a neurologist for evaluation. Blood JCV (PCR and/or JCV antibody testing) should be performed. If indicated, cerebrospinal fluid (CSF) JCV testing should also be performed. Magnetic resonance imaging (MRI) is strongly recommended. If test results are negative, the investigator should contact the Sponsor for appropriate action to be taken. If PML is confirmed, the subject should be withdrawn from treatment, proceed to the Follow-Up Period, and be followed until resolution. Serum banked from the Baseline visit may also be tested for JCV as part of the PML work-up.

There are no known tests that can reliably determine who is at increased risk for developing PML. There are no known interventions that can reliably prevent PML or adequately treat PML if it occurs.

The basic components of this monitoring include:

1. Prior to study start, the Sponsor will provide information regarding PML and its presentation.
2. Qualified site staff will administer the Neurological Symptoms Questionnaire at every visit.
3. In the event of positive symptoms on the Neurological Symptoms Questionnaire, the investigator will contact the medical monitor and the subject will be referred to a neurologist.

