4. Any case of suspected or confirmed PML will go through independent PML adjudication and an opinion will be provided to the Sponsor. The independent PML adjudicator can request additional testing and further data collection.

Figure 11-1 Algorithm for PML Monitoring

[figure not shown]

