11.5. Appendix 5 – Neurological Symptoms Questionnaire

[figure not shown]
		YES	NO
1.	Does the subject report any new focal weakness?		
2.	Does the subject report any new difficulty with coordination or walking?		
3.	Does the subject report any new signs of confusion, impaired memory, or attention?		
4.	Does the subject appear apathetic compared to previous contacts?		
5.	Does the subject report any new visual disturbances?		
6.	Has the subject had any new trouble speaking, either slurring speech, difficulty getting out words, difficulty understanding words, or difficulty comprehending spoken language?		
7.	Does the subject have any other new neurological symptoms, including but not limited to: 
• New onset seizure• New sensory loss• New emotional lability		

[figure not shown]
If any of the above are answered “Yes” at any visit, the investigator will contact the medical monitor.

Any neurological symptom that cannot be directly attributed to a concurrent medical condition or concomitant medication **must be referred to a neurologist.**

ABSIS SCORING SHEET

Date:
Patient's weight (kg):

Legend for weighting factor (most dominant appearance of skin lesions):	
1.5	Erosive, exudative lesions
1	Erosive, dry lesions
0.5	Reepithelialized lesions

Skin Involvement (Max BSA)	Patient's BSA	Weighting factor
Head & neck (9%):		
L Arm including hand (9%):		
R Arm including hand (9%):		
Trunk (front & back) (36%):		
L Leg (18%):		
R Leg (18%):		
Genitals (1%):		

(Skin involvement total score: % BSA x weighting factor = 0-150 points)

Oral Involvement:

I. Extent (enter 1 for presence of lesions, 0 absence of any lesion):

Upper gingival mucosa		Tongue	
Lower gingival mucosa		Floor of the mouth	
Upper lip mucosa		Hard palate	
Lower lip mucosa		Soft palate	
Left buccal mucosa		Pharynx	
Right buccal mucosa			

[figure not shown]
(Total score ranges from 0-11)

[figure not shown]
Severity (discomfort during eating/drinking)

[figure not shown]
Food	Level	Factor of Discomfort	Severity score
Water	1		
Soup	2		
Yogurt	3		
Custard	4		
Mashed potatoes/ scrambled egg	5		
Baked fish	6		
White bread	7		
Apple/ raw carrot	8		
Fried steak/ whole-grain bread	9		

[figure not shown]
(Severity score= Level multiplied by the factor of discomfort= 0-45 points)

[figure not shown]
Legend for factor of discomfort	
1	Pain/bleeding occurred always
0.5	Pain/bleeding occurred sometimes

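### Section 4.4.1 does not make its dose-resume rule subject to Appendix 4, so for PML-consistent symptoms that clear within a week the two texts give different restart instructions

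*Protocol*

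**What the plan says.** Protocol Section 4.4.1 names three reasons to hold a dose: neutropenia below a stated count, suspected serious systemic infection, and positive symptoms on the neurological questionnaire. The third bullet refers to Appendices 4 and 5. A single rule then covers all three. For early recovery: "If the condition resolves within 1 week, administer the held dose and then return to the regular dosing schedule". For later recovery the dose is skipped and, "after the condition resolves, return to the regular dosing schedule". The only consultation that the section itself names is with the medical monitor, once at least two doses in a row have been missed.

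Appendix 4 deals with neurological signs or symptoms consistent with PML. There, "treatment should be halted and the subject referred to a neurologist for evaluation". Blood is tested for JCV, cerebrospinal fluid is tested if indicated, and MRI is strongly recommended. A negative work-up does not restart dosing by itself: "If test results are negative, the investigator should contact the Sponsor for appropriate action to be taken". Confirmed PML leads to withdrawal from treatment.

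Several safeguards surround this. Under Appendix 5, after any positive answer "at any visit, the investigator will contact the medical monitor". Appendix 4 adds: "Any case of suspected or confirmed PML will go through independent PML adjudication and an opinion will be provided to the Sponsor". Section 6.3.2.3 lists PML as an event of special interest and sends suspected cases to the Appendix 4 algorithm. Section 4.4.2 defers to Appendix 4 for permanent discontinuation.

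**The concern.** Section 4.4.1 makes resolution of the condition the only test for restarting. That suits neutropenia, where a blood count shows recovery. It suits PML-consistent symptoms less well, because there Appendix 4 asks for an evaluation and not only for the symptoms to go away. The reference to Appendices 4 and 5 sits on the bullet that triggers the hold; the restart sentences carry no exception.

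A site working from the dose-holding section alone could therefore give a further dose of a B-cell-depleting drug while Appendix 4 would keep the subject off treatment. Appendix 4 itself acknowledges that nothing known dependably prevents PML or treats it adequately, so the restart condition deserves to be explicit.

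**Working it through.** The plan states no figure to reproduce. The check compares the texts on one case and then prices the fix.

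**1. Can both texts apply to the same subject?** Yes. Appendix 4 states: "Signs and symptoms of PML include visual disturbances". Appendix 5, item 5, asks: "Does the subject report any new visual disturbances". A positive answer to that item triggers the Section 4.4.1 hold, and the symptom can also be one that Appendix 4 treats as consistent with PML. Items 2 (coordination or walking) and 3 (confusion, memory or attention) likewise correspond to ataxia and mental status change in Appendix 4. This shows only that the case can arise.

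**2. Worked case.** A new visual disturbance, with no other evident cause, is reported at the Week 12 dosing visit. SAP Table 9-1 puts that visit at Day 85. The symptom is gone by Day 91. The 1-week limit is 85 + 7 = Day 92.

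| Step | Section 4.4.1, read literally | Appendix 4, visible text |
|---|---|---|
| At the positive answer | Hold the dose | Halt treatment, contact the medical monitor, refer to a neurologist |
| Symptom gone at Day 91 | Give the held dose by Day 92 | No restart on resolution alone; referral and JCV testing still apply |
| Tests negative | Not mentioned | Contact the Sponsor for the next step |

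The texts agree on stopping and differ on restarting. The later-recovery branch of Section 4.4.1 has the same feature: the dose is skipped, but resumption still depends only on resolution.

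**3. Cost of waiting for the evaluation.** Inputs: 17 planned injections over 15 dosing visits 4 weeks apart, with two injections at Weeks 0 and 4 and one at each other visit. The documents give no duration for the evaluation, so it is varied as an assumption. With k skipped single-injection visits, the share missed is k/17 and the gap between doses is 4 × (k + 1) weeks.

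| Assumed evaluation time | Visits skipped (k) | Injections missed | Gap between doses |
|---|---|---|---|
| Up to 1 week | 0 | 0 | No skipped visit |
| Over 1 to 4 weeks | 1 | 1/17 = 5.9% | 8 weeks |
| Over 4 to 8 weeks | 2 | 2/17 = 11.8% | 12 weeks |
| Over 8 to 12 weeks | 3 | 3/17 = 17.6% | 16 weeks |

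If the hold starts at the two-injection Week 4 visit, the shares for k = 1, 2 and 3 become 2/17 = 11.8%, 3/17 = 17.6% and 4/17 = 23.5%. All are upper bounds on the added cost, because Section 4.4.1 already skips a dose when symptoms last more than 1 week.

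**The case against.** The strongest reply is that the protocol, read as a whole, already answers the question. The hold bullet cites Appendices 4 and 5. Section 6.3.2.3, in the main body, makes the Appendix 4 algorithm the procedure for suspected PML. Medical monitor contact follows every positive answer, and suspected cases are adjudicated independently. A site that follows these pointers keeps treatment halted. The texts can even be reconciled if a condition counts as resolved only when the Appendix 4 work-up has cleared it. All of this stands, and it limits the point to wording. It does not remove the point: Section 4.4.1 does not define resolution that way, and the visible text makes neither the contact nor the adjudication a precondition for giving the held dose.

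Second, Figure 11-1 is the PML algorithm itself and is not shown. The Amendment 5 change log says that dose-holding for positive symptoms was already in that algorithm, so the figure may contain a restart step. A reader might infer that the protocol has no restart condition for neurological holds; the documents do not support that, because the figure cannot be checked.

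Third, many positive answers will not concern PML. Subjects enter on 20 mg/day of prednisone or more, and Section 1.2 names neuropsychiatric changes among steroid side effects. Amendment 5 deliberately eased neurologist referral where a symptom has an identifiable cause. Requiring Sponsor or medical monitor agreement after every positive answer would turn an existing contact into a new approval step and reach beyond the problem. This objection is correct, and it sets the scope of the fix.

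**Conclusion.** The point holds as a wording conflict between the restart sentences of Section 4.4.1 and the visible text of Appendix 4, confined to symptoms consistent with PML. A reader might infer that the plan directs sites to re-dose suspected PML, or that nobody oversees such cases. Neither is supported, given the cross-references, the medical monitor contact and the adjudication.

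No rate of premature re-dosing can be given, because the documents do not report how often the questionnaire is positive or how often symptoms clear within a week. The overlap between questionnaire items and PML signs is not a measure of risk either, since the Appendix 4 halt depends on clinical judgement that symptoms are consistent with PML. What makes the point worth acting on is the severity of the possible outcome set against a one-sentence remedy.

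The conclusion rests on a literal reading of resolution as symptom resolution, and on Figure 11-1 not already settling the matter. Practical reach is limited: the protocol reports that the pemphigus vulgaris program has been terminated, and the SAP that the study stopped early, so the change matters only for dosing still given under this text.

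**What to change.** Add one sentence to Section 4.4.1: *For holds due to positive neurological symptoms, the resume/skip rule is subject to Appendix 4: where symptoms are consistent with PML, no dose is given, even if symptoms have resolved, until the Appendix 4 evaluation is complete and the Sponsor has been contacted.* If Figure 11-1 already contains a restart step, refer to that step instead. Leave the existing rule unchanged for neutropenia, for infection and for neurological symptoms attributed to another cause.

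No new test, visit or approval is needed: Appendix 4 already asks for the evaluation in these subjects, and for Sponsor contact when results are negative. The downside is an occasional skipped dose while the evaluation is completed. A long evaluation could weaken B-cell depletion: two skipped visits make a 12-week gap, and Section 3.3 reports that dosing every 12 weeks at 3 to 60 mg left suppression incomplete in the multiple sclerosis study. The same section predicts a median of about 28 weeks after dosing stops before B cells return to the lower limit of normal, so full repletion over one to three skipped visits would not be typical.
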